1.4.2 Primary Endpoint 2 Results

The purpose of primary endpoint 2 is to evaluate the LV lead pacing threshold for the permanently programmed pacing vector at 3 months post-implant. Specifically, the percentage of subjects with an acceptable LV pacing threshold in the permanently programmed vector at the 3 month follow-up will be determined. An acceptable LV threshold was defined as being ≤ 2.5 V at a pulse width of 0.4 ms in the pacing vector programmed at the beginning of the 3 month follow-up.

For the purposes of the primary endpoint 2 analysis, evaluable subjects are those who were included in the pre-market cohort and either completed a threshold test at a pulse width of 0.4 ms at the 3 month follow-up (n = 276), did not have a threshold test at or missed the 3 month follow-up but had Home Monitoring data meeting specific consistency criteria available for imputation (n = 3), had a subsequent follow-up visit with threshold test at a pulse width of 0.4 ms (n = 7), or were not successfully implanted due to a Sentus QP lead related adverse event (n = 0). A total of 286 subjects were included in the evaluation of primary endpoint 2.

[figure not shown]
Analysis

Primary endpoint 2 was evaluated by performing an exact, binomial test comparing the observed proportion (rate of acceptable LV pacing thresholds at 3 months) to 88.0%.

Of the 286 evaluable subjects for primary endpoint 2, 267 subjects had an acceptable LV threshold for a rate of 93.4%, 95% CI of 89.8% to 96.0%, p=0.002.

Figure 7 provides a histogram showing the Sentus QP pacing threshold values in the permanently programmed vector at 3 months. The acceptable threshold maximum of 2.5 V is indicated by the vertical line. Three subjects had a result of no capture possible during the threshold test and are not displayed in Figure 7. These three subjects were considered as failures in the analysis of primary endpoint 2.

Figure 7: Sentus QP Pacing Threshold Values at the 3 Month Follow-up

Conclusion

The results indicate that the proportion of subjects with an acceptable threshold value in the permanently programmed vector at the 3 month follow-up is greater than 88.0%; therefore, primary endpoint 2 is met.

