2.3.3 Primary Endpoint 2 Analysis

For primary endpoint 2, only subjects who provide informed consent, met the enrollment criteria, and in whom a Sentus QP lead was successfully implanted will be included. The common scenarios listed below will be taken into account for analysis of primary endpoint 2.

- Any subjects not successfully implanted due to a Sentus QP lead related adverse event will be included in the analysis for primary endpoint 2 as a failure.
- For successfully implanted subjects that missed a 3 month visit or did not undergo threshold testing of the LV lead at the 3 month visit, or completed threshold testing at a pulse width other than 0.4 ms, missing data points will be imputed according to Section 2.5.4.

Primary endpoint 2 will be evaluated by performing an exact, binomial test comparing an observed proportion (rate of acceptable LV pacing thresholds at the permanently programmed pacing vector at 3 months) to 88.0%. The lower, two-sided 95% confidence bound for the percentage of subjects with an acceptable LV pacing threshold in the permanently programmed pacing vector must be greater than 88.0%.

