2.4 Estimated Sample Size

2.4.1 Pre-Market Analyses

The sample size required to evaluate primary hypotheses 1 and 2 was estimated using the following design criteria:

- Study design: non-randomized
- Test basis: exact binomial test
- Type I error, alpha: 2.5% (one-sided)
- Statistical power: 80% for acceptance of both primary Alternative hypotheses

For primary safety hypothesis (complication-free rate), the following assumptions apply:

- Expected complication-free rate through 6 months: 95.0%
- H_A: Complication-free rate through 6 months post-implant > 90.0%

For primary efficacy hypothesis (LV pacing threshold for permanently programmed vector), the following assumptions apply:

- Expected rate of acceptable LV pacing thresholds at 3 months: 93.0%
- H_A: Acceptable LV pacing threshold rate at 3 months > 88.0%

Based on the above criteria, a total of 231 evaluable subjects assessed at 6 months would be required to accept the primary safety alternative hypothesis (endpoint 1). For primary endpoint 2, a total of 282 evaluable subjects assessed at 3 months would be required to accept the primary efficacy alternative hypothesis.

An adjustment of 10% is used in the sample size estimation for both primary endpoints 1 and 2 to account for subjects that exit the clinical investigation prior to having a 6 month evaluation. Reasons that subjects may exit the clinical investigation include withdrawal of consent, mortality, device explant, change in physician, or subject moving. Therefore, up to 314 subjects (=282/.9) will need to be enrolled to account for premature study terminations.

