11.1.2 MultiPole Pacing (MPP) Description

[figure not shown]
The US market released MultiPole Pacing feature of the Ilivia HF-T QP family CRT-D systems allows left ventricular pacing in two different vectors within a single cardiac cycle using the same quadripolar lead in order to improve synchronization of the contraction pattern. Both left ventricular stimuli will either be before the right ventricular pace (1st LV – 2nd LV - RV) or after the right ventricular pace (RV-1st LV – 2nd LV). The second LV stimulus will only be capable of delivering the second pacing stimulus in the left ventricle; sensing and timing will not be affected by 2nd LV. The delay between the two left ventricular paces is programmable between 0 ms and 50 ms in 5 ms steps. All 12 currently approved pacing configurations are available for both pacing stimuli. However, the same pacing vector cannot be used for both stimuli. Pacing output and interventricular delays can be programmed independently. There is no change to the same parameter ranges available for pacing amplitude and pulse width (0.5 to 7.5 V and 0.4 to 1.5 ms, respectively). The programmable parameters for the MultiPole Pacing feature are listed in 11.

Table 11: Programmable Parameters for MultiPole Pacing

Parameter	Programmable range
LV MultiPole stimulation	OFF, 1st LV-2nd LV-RV, RV-1st LV-2nd LV
LV stimulation amplitude (1st LV and 2nd LV)	0.5 to 7.5 V
LV stimulation width (1st LV and 2nd LV)	0.4 to 1.5 ms
Interval 1st LV – 2nd LV	0 to 50 ms
Stimulation configuration (1st LV and 2nd LV)	LV1 Tip → LV2 Ring LV1 Tip → LV4 Ring LV1 Tip → RV Coil LV1 Tip → ICD LV2 Ring → LV1 Tip LV2 Ring → LV4 Ring LV2 Ring → RV Coil LV3 Ring → LV2 Ring LV3 Ring → LV4 Ring LV3 Ring → RV Coil LV4 Ring → LV2 Ring LV4 Ring → RV Coil

MultiPole Pacing is programmable using programmer software that can be used with one of BIOTRONIK’s programmers, either the ICS 3000 (P950037/S035, dated May 18, 2005) or the Renamic (P950037/S089, dated April 15, 2011). The user accesses the feature from the Bradycardia/CRT parameters tab (Figure 9).

Figure 9: Programming MultiPole Pacing

As shown in Figure 9 and Figure 10 the polarity, pulse amplitude, and pulse width for the two LV stimuli can be programmed independently.

Figure 10: Programming 1st LV Stimulus

[figure not shown]

Figure 11: Programming 2nd LV Stimulus

[figure not shown]

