14. APPENDIX A: DEFINITION OF TERMS

Abnormal Defibrillation Impedance – Defibrillation impedance is typically considered abnormal if a measurement is $< 25 \Omega$ or $> 150 \Omega$ (based on lead model and measurement range of the device). Includes high or low shock impedance when attempting to deliver a shock.

Abnormal Pacing Impedance – Pacing impedance is typically considered abnormal if a measurement is $< 200 \Omega$ or $> 3000 \Omega$ (based on lead model and measurement range of the device).

Cardiac Perforation associated with a lead – Penetration of the lead tip through the myocardium (including microperforation), clinically suspected and confirmed by chest x-ray, fluoroscopy, echocardiogram, intracardiac electrogram and/or visually.

Clinical Lead Failure – Inability of the lead to correctly sense or pace in the heart, not attributable to a mechanical or electrical failure of the lead or pulse generator and that remains unresolved despite reprogramming and/or repositioning.

Coronary Sinus Dissection – A tear that occurs in the wall of the coronary sinus.

Electrical Lead Failure – Confirmed or suspected lead issue that is due to an electrical failure of the lead, such as electrical noise not attributable to other causes, and that leads to loss of pacing and/or sensing. Specific types of confirmed or suspected electrical lead failures, such as high impedance values, no capture, and loss of sensing, are separate adverse event categories and should only be reported once. Confirmed or suspected electrical lead failures caused by induced malfunctions, such as lead damage caused during a procedure, are excluded.

Elevated Pacing Threshold – Either of the following is considered an elevated pacing threshold for the Sentus QP lead:

- At implant: pacing threshold $> 3.0 \text{ V}$ at 0.4 ms or 0.5 ms
- At routine evaluation: pacing threshold $> 2.5 \text{ V}$ at 0.4 ms or 0.5 ms

These thresholds are less than half of the maximum output in BIOTRONIK CRT devices and allow for an adequate safety margin.

Extracardiac Stimulation – Clinical observation of inadvertent nerve/muscle stimulation other than cardiac muscle, such as phrenic nerve stimulation.

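### Section 2.3.3 sends every 3-month LV threshold test not done at 0.4 ms to imputation, even when the reading at a longer pulse width already establishes failure, so a known endpoint 2 failure can be rescored as a success

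*Combined protocol and SAP*

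**What the plan says.** Sections 1.4.2 and 2.2.2 define an acceptable result as an LV threshold of 2.5 V or less at 0.4 ms, in the vector programmed when the 3-month interrogation begins.

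Section 2.3.3 groups three situations for successfully implanted subjects: the visit was missed, no LV threshold test was done, "or completed threshold testing at a pulse width other than 0.4 ms, missing data points will be imputed according to Section 2.5.4". The third differs from the other two because a 3-month measurement exists. The rule does not look at its value.

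Section 2.5.4 then gives the order of imputation. A Home Monitoring value from the visit day, the due date or the nearest day comes first. For endpoint 2 that value is checked for consistency against six surrounding values. If no Home Monitoring data are available, the threshold from the next completed follow-up may be used. Neither route requires comparison with the discarded in-clinic reading. The later-visit route does not require the same vector or the absence of reprogramming or lead revision in between, and Section 3.2.6 lets the physician change the vector after testing. Further analyses of imputed data are to be done only as needed; none is specified.

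Section 11.1.2 gives the programmable ranges as "pacing amplitude and pulse width (0.5 to 7.5 V and 0.4 to 1.5 ms, respectively"), so 0.4 ms is the shortest width. Appendix A introduces two cases with "Either of the following is considered an elevated pacing threshold for the Sentus QP lead"; at routine evaluation the case is a threshold above 2.5 V at either 0.4 ms or 0.5 ms.

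Section 1.4.2 reports 276 subjects tested at 0.4 ms at the 3-month visit, 3 imputed from Home Monitoring, and those who "had a subsequent follow-up visit with threshold test at a pulse width of 0.4 ms (n = 7").

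**The concern.** An off-width reading is not always uninformative. A subject with a threshold of, say, 3.0 V at a longer width in the programmed vector would be expected to need at least 3.0 V at 0.4 ms. The endpoint result is then known, yet the rule labels it missing and allows another value to stand in for it. That value may come from a later visit, possibly in a different vector.

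The error has one direction. The correct score for such a subject is failure; the imputed score is either failure or success. The acceptable-threshold rate can therefore only stay the same or rise. The endpoint is a single-arm comparison with a fixed goal, and a small number of rescored subjects could decide it.

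**Working it through.** **Inputs.** The test is an exact binomial, "comparing an observed proportion (rate of acceptable LV pacing thresholds at the permanently programmed pacing vector at 3 months) to 88.0"%, and the lower two-sided 95% bound must exceed that figure (2.3.3). Section 2.4.1 gives "Type I error, alpha: 2.5% (one-sided"), "Statistical power: 80% for acceptance of both primary Alternative hypotheses", and "Expected rate of acceptable LV pacing thresholds at 3 months: 93.0"%. The required evaluable number is 282. The reported result is 267/286 (1.4.2).

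**Step 1: reproduce the plan's figures.**
- For n = 282, the smallest r with P(X ≥ r | 282, 0.88) ≤ 0.025 is r = 259, with exact alpha 0.0246. Power for endpoint 2 alone is P(X ≥ 259 | 282, 0.93) = 0.812. No smaller n reaches 80%. 282/0.9 = 313.3, rounded up to 314.
- Evaluable subjects: 276 + 3 + 7 + 0 = 286, of whom 3 + 7 = 10 were imputed.
- 267/286 = 93.36%, Clopper-Pearson 89.82% to 95.95%, one-sided exact p = 0.00198.

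All agree with the documents.

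**Step 2: which off-width readings are decisive.** Let T(w) be the capture threshold at pulse width w, and assume that T does not increase with w. For w > 0.4 ms:
- If T(w) > 2.5 V, or there is no capture, then T(0.4) ≥ T(w) > 2.5 V: failure.
- If T(w) ≤ 2.5 V, T(0.4) may lie on either side of 2.5 V: undetermined, and imputation is reasonable.

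**Step 3: pass mark at n = 286.** The smallest r with P(X ≥ r | 286, 0.88) ≤ 0.025 is 263. The reported 267 exceeds it by 4.

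**Step 4: recode k imputed successes as failures, n held at 286.** The value of k is not in the documents. It cannot exceed 7 if only later-visit imputations are affected, or 10 if all are.

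| k | Acceptable | Rate | Lower 95% bound | One-sided p | Endpoint 2 |
|---|---|---|---|---|---|
| 0 | 267/286 | 93.4% | 89.8% | 0.002 | met |
| 1 | 266/286 | 93.0% | 89.4% | 0.004 | met |
| 4 | 263/286 | 92.0% | 88.2% | 0.020 | met |
| 5 | 262/286 | 91.6% | 87.8% | 0.032 | not met |
| 7 | 260/286 | 90.9% | 87.0% | 0.073 | not met |
| 10 | 257/286 | 89.9% | 85.8% | 0.192 | not met |

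**The case against.** The strongest reply is that no affected subject is shown. Section 1.4.2 does not divide the 10 imputed subjects into missed visits, absent tests and off-width tests. To reverse the result, at least 5 of the 10 must have had an off-width reading in the programmed vector, with a value above 2.5 V or no capture, and then been scored acceptable. At the overall failure rate, 10 subjects would yield only 10 × 19/286 ≈ 0.7 failures. This stands. It limits the point to what the rule permits.

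Home Monitoring is the first-line source and can supply a same-day value, although the later-visit fallback was used for 7 of the 10. Three subjects with no capture possible were counted as failures, so not every bad result was replaced; their pulse width is not given, and Section 2.3.3 would not secure that scoring at another width.

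The physical assumption is also not stated in the documents. Appendix A is consistent with it for 0.5 ms, but it is a glossary and not an endpoint scoring rule. The range in Section 11.1.2 describes programmable stimulation settings and not threshold-test widths as such.

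Three stronger inferences are tempting but unsupported:
- A reader might subtract 276 from 282 and conclude that at least 6 completed 3-month visits lacked a 0.4 ms test. The 282 is the count of completed visits that triggered the analysis, while the 276 belong to a cohort of 299 defined by implant date (1.4, 2.3.1). The sets differ, so the difference is not a bound.
- A reader might infer that longer widths were chosen because the 0.4 ms threshold was poor. Nothing in the documents says so, and 0.5 ms appears as an ordinary test width in the predecessor-lead registry (Table 13).
- A reader might extend the point to secondary endpoint 1. Section 2.3.5 restricts its main analysis to subjects with 3-month data, so the replacement mechanism does not arise there.

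**Conclusion.** The rule is wrong for one identifiable class of readings: a 3-month test in the programmed vector at a width longer than 0.4 ms that shows more than 2.5 V or no capture. It lets a known failure become a success, and its effect on the acceptable rate is upward or nil. This rests on the capture threshold not rising with pulse width, and on test widths sharing the 0.4 ms lower limit of the programmable range.

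The actual effect is unknown, with 0 to 10 subjects affected and possibly none. The reported conclusion survives up to 4 recoded successes and not 5. A reader might infer that the endpoint 2 result is unsound; the documents do not support that, because they give neither the number nor the values of any off-width readings. The planned sample size is unaffected.

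**What to change.** In Section 2.3.3, state that a 3-month reading in the programmed vector at a pulse width longer than 0.4 ms is scored as a failure if it exceeds 2.5 V or shows no capture. Reserve imputation under Section 2.5.4 for longer-width readings of 2.5 V or less and for subjects with no 3-month test.

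Endpoint 2 was analysed and submitted before this protocol version, so the revised scoring should not replace the reported primary result. Report it as a labelled sensitivity re-analysis. For each of the 10 imputed subjects, tabulate the reason for imputation, any off-width reading with its pulse width and vector, the substituted value and its source, and the score under both rules.

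The cost is a short addition to Section 2.3.3 and a review of 10 existing records. The downside is that the stated rate may become slightly less favourable.

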2.3.4 Primary Endpoint 3 Analysis

The analysis population for primary endpoint 3 will include all subjects who provided informed consent, met the enrollment criteria, and in whom a Sentus QP lead was successfully implanted. Only subjects who were successfully implanted and completed a 60-month month visit will be included in the endpoint analysis

Primary endpoint 3 will be evaluated by performing an exact, binomial test comparing the observed proportion (overall complication-free rate at 5 years) to the performance goal of 92.5%. The lower, two-sided 95% confidence bound for the overall complication-free rate must be greater than 92.5%.

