The purpose of primary endpoint 3 is to evaluate the long-term Sentus QP related complication-free rate through 5 years post-implant. The Sentus QP related complications that will be assessed in this primary endpoint are defined in Section 6.6.2. The parameter of interest $p_{Complication}^{SentusQP}$ is the complication-free rate per subject, which will be calculated by (1 - the number of subject with one or more complications divided by the number of subjects) in percent. The period of observation starts after successful implantation of the Sentus QP lead.

The following hypotheses have been defined to evaluate the primary endpoint “Sentus QP related complication-free rate through 5 years”:

H_0 : Complication-free rate through 5-years post-implant is $\leq 92.5\%$

H_a : Complication-free rate through 5-years post-implant is $> 92.5\%$

A rejection of the null hypothesis (H_0) would demonstrate evidence that the complication-free rate is greater than 92.5%.

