2.4.2 Post-Approval Analysis

The sample size required to evaluate primary hypotheses 3 was estimated using the following design criteria:

- Study design: non-randomized
- Test basis: exact binomial test
- Type I error, alpha: 2.5% (one-sided)
- Statistical power: 80%
- Expected complication-free rate through 5-years: 94.75%

- H_A: Complication-free rate through 5-years post-implant > 92.5%

Based on the above criteria, a total of 979 evaluable subjects assessed at 5 years would be required to accept the primary 5-year safety alternative hypothesis.

An adjustment of 11% per year is used in the sample size estimation for primary endpoint 3 to account for subjects that exit the clinical investigation prior to having a 5-year (60-month) evaluation. Reasons that subjects may exit the clinical investigation include withdrawal of consent, mortality, device explant, change in physician, or subject moving. Therefore, up to 1754 evaluable subjects ($=979/0.89^5$) will need to be enrolled to account for premature study terminations.

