3.5 Study Participation Expectations

3.5.1 Point of Enrollment

A subject is considered enrolled in the QP ExCELS study upon signing the Informed Consent Form and meeting the inclusion/exclusion criteria at time of consent.

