4.6.1 Protocol Violations

Protocol violations are defined as instances where the protocol requirements and/or regulatory guidelines were not followed, and are generally more serious in nature. Protocol violations are considered to potentially affect the scientific soundness of the study and/or the rights, safety, or welfare of subjects. Protocol violations include, but are not limited to, failure to obtain consent, unapproved investigator implanting an investigational device, and subject inclusion/exclusion violations.

The investigator must notify the reviewing IRB of all protocol violations per the reporting requirements. In some instances, such as failure to obtain consent, the investigator should also seek guidance from the IRB to ensure the subject received appropriate information to consider their participation in the study.

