In addition, the following procedure-related adverse events will be included in the analysis of primary endpoint 1:

- Pneumothorax directly associated with the Sentus QP lead

- Cardiac perforation with or without tamponade caused by the Sentus QP lead
- Coronary sinus dissections directly caused by the Sentus QP lead (e.g., dissections caused by lead delivery device are excluded)

Finally, subject deaths resulting from a Sentus QP lead-related AE will be included in the primary endpoint analysis.

6.6.2 Adverse Events Included in Primary Endpoint 3

ADEs related to the Sentus QP lead and resolution combinations that will be analyzed as part of the primary endpoint 3 ($p_{\text{Complication}}^{\text{SentusQP}}$) are presented in Table 8. Combinations marked with an “X” will be included but are not limited to the primary endpoint 3 analysis. All Sentus QP related ADEs meeting the below criteria occurring after successful implantation until the 60-month post-implantation visit will be included.

Table 8: Adverse Event/Resolution Combinations for Primary Endpoint 3 Analysis

Resolution	Clinical lead failure	Electrical lead failure	High pacing threshold excluding events within 45 days of implant or lead revision	Extracardiac stimulation	Intermittent capture excluding events within 45 days of implant or lead revision	Lead dislodgement >45 days post-implant or lead revision	Lead impedance out of range, high	Lead impedance out of range, low	Lead undersensing	Lead-related thrombosis	Loss of sensing	Mechanical lead failure	No capture excluding events within 45 days of implant or lead revision
Lead surgically repositioned	X	X	X	X	X	X	X	X	X	X	X	X	X
Lead surgically explanted	X	X	X	X	X	X	X	X	X	X	X	X	X
Lead surgically replaced	X	X	X	X	X	X	X	X	X	X	X	X	X
Lead surgically abandoned	X	X	X	X	X	X	X	X	X	X	X	X	X
Other lead-related surgery performed	X	X	X	X	X	X	X	X	X	X	X	X	X
Lead pacing polarity or mode reprogrammed*		X										X	
Lead electrically abandoned and pacing disabled	X	X										X	
Lead use continued based on medical judgment	X	X										X	

*Adverse events resolved by reprogramming of pacing polarity or pacing mode are only included in primary endpoint 3 analysis in cases of electrical or mechanical lead failure. Other adverse events, such as extracardiac stimulation, which are resolved by reprogramming are excluded.

In addition, the following adverse events will be included in the analysis of primary endpoint 3:

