Centralized monitoring is conducted via investigator locked electronic case report forms (eCRFs) through the source data verification of source documents uploaded to the eCRF. Some examples of data that may be monitored remotely include: informed consent forms, enrollment, eligibility, implant, study termination, device data and adverse events reported in the EDC system. Sites are required to support centralized monitoring by providing source documents to BIOTRONIK in order to source data verify data reported in the EDC system and resolving queries in a timely manner. Uploaded source documents should meet ALCOA principles of attributable, legible, contemporaneous, original, and accurate. It is critical that the fully executed informed consent form and all necessary source documentation are uploaded to the EDC in a timely manner.

The entries in the eCRF will be reviewed and source data verified by on-site or centralized monitors (authorized BIOTRONIK, Inc. personnel, or by authorized BIOTRONIK, Inc. designees) to ensure that the investigator and the clinical investigation team conducts the clinical investigation in accordance with the clinical investigation protocol and applicable FDA and local laws and regulations

to ensure adequate protection of the rights, safety and wellbeing of subjects and the quality and integrity of the resulting data. In addition, BIOTRONIK, Inc. may require the presence of personnel from BIOTRONIK, Inc. at implant and/or follow-up visits outlined in this protocol in order to assist the investigator and other site personnel.

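### Primary endpoint 3 leaves implanted subjects with an eligibility violation out of the 5-year lead safety rate, while secondary endpoints 7 and 8 set no such condition

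*Combined protocol and SAP*

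**What the plan says.** Section 2.3.4 defines the endpoint 3 population as one that "will include all subjects who provided informed consent, met the enrollment criteria, and in whom a Sentus QP lead was successfully implanted". It then adds a second restriction: "Only subjects who were successfully implanted and completed a 60-month month visit will be included in the endpoint analysis". Section 2.2.3 defines the parameter as "1 - the number of subject with one or more complications divided by the number of subjects", and the rate is tested against a goal of 92.5%.

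Other sections bear on the eligibility clause:

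- Section 4.6.1 gives examples of protocol violations that include "unapproved investigator implanting an investigational device, and subject inclusion/exclusion violations". The reasons for study termination in 3.5.2 do not include an eligibility violation, so a violator can be implanted and followed.
- Section 2.3.5 defines the population for secondary endpoints 7 and 8 by successful implantation and the 60-month visit only. Meeting the enrollment criteria is not required. Under 2.2.4.8, endpoint 8 breaks down the event types that make up primary endpoint 3.
- Section 6.6.2 says: "All Sentus QP related ADEs meeting the below criteria occurring after successful implantation until the 60-month post-implantation visit will be included". It sets no eligibility condition.
- Section 3.5.1 treats a subject as "considered enrolled in the QP ExCELS study upon signing the Informed Consent Form and meeting the inclusion/exclusion criteria at time of consent". Section 2.5.4 words its Kaplan-Meier censoring rule for enrolled subjects.

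**The concern.** A device safety rate is meant to describe what happens to people who receive the device. A subject implanted in breach of a criterion, such as an earlier attempt to place a left ventricular lead, carries the same lead for the same five years. Read as written, 2.3.4 removes that subject from the primary rate, and with the subject any dislodgement, failure or revision that would otherwise count against 92.5%.

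The plan is also inconsistent with itself. Endpoint 8 is supposed to decompose endpoint 3, yet its population is wider on eligibility. A violator who completes 60 months and has a qualifying complication counts in endpoint 8 and not in endpoint 3, so the components need not add up to the whole.

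If violators have more lead complications than other subjects, leaving them out makes the goal easier to meet than the nominal 2.5% implies.

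**Working it through.** **Inputs from 2.4.2:** goal 92.5%, expected rate 94.75%, one-sided alpha 2.5%, power 80%, exact binomial test, 979 evaluable, 11% attrition per year. **Assumed, because the documents are silent:** the share v of violators among the 979, and their complication rate c.

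**1. The plan's own figures.** The one-sample normal approximation is n = [(1.960·√(0.925·0.075) + 0.842·√(0.9475·0.0525)) / 0.0225]² = 978.8, which rounds up to 979. Inflation gives 979/0.89⁵ = 1753.2, so 1754. Both figures reproduce.

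**2. Pass mark at n = 979.** At most 57 subjects may have a complication (922 free, exact lower bound 92.52%). With 58 the bound is 92.41% and the goal is missed. Exact one-sided error is 2.4% and exact power is 81%.

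**3. Adding excluded subjects back at that boundary.**

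| Added back | With a complication | Free / total | Lower bound | Goal met |
|---|---|---|---|---|
| 10 | 0 | 932/989 | 92.60% | yes |
| 10 | 1 | 931/989 | 92.48% | no |
| 20 | 1 | 941/999 | 92.56% | yes |
| 20 | 2 | 940/999 | 92.45% | no |
| 49 | 3 | 968/1028 | 92.55% | yes |

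A handful of subjects can change the result at the boundary, in either direction.

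**4. Error rate if the true all-implanted complication rate is 7.5%.** The eligible-only complication rate is (0.075 − v·c)/(1 − v). The test is run on 979·(1 − v) subjects, with the pass mark recomputed for that n.

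| v | Analysed n | Max. failures | Eligible rate, c = 15% | P(goal met), c = 15% | P(goal met), c = 7.5% (equal rates) |
|---|---|---|---|---|---|
| 1% | 969 | 56 | 7.42% | 2.6% | 2.1% |
| 2% | 959 | 55 | 7.35% | 2.9% | 1.9% |
| 5% | 930 | 53 | 7.11% | 5.1% | 1.9% |

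**5. Shift in the reported rate at the planned 94.75%.** If violators have twice the 5.25% complication rate of eligible subjects, excluding them raises the reported rate by v × 5.25 points: 0.11 points at 2% violators and 0.26 at 5%. At equal rates the shift is zero.

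**The case against.** The strongest point on the other side is how the same clause appears to have been applied. Sections 2.3.2 and 2.3.3 carry the same eligibility wording for endpoints 1 and 2. The evaluable counts reported in 1.4.1 (279) and 1.4.2 (286) are built from visits, events, imputation and implant success, with no eligibility exclusion listed. That does not settle endpoint 3, but it is the only evidence in the documents, and it suggests the clause may remove few or no subjects. Next, 6.6.2 can be read as defining which events count while 2.3.4 defines whose events count. On that reading the two need clarification and do not flatly conflict. The 60-month completer rule in the same section is also likely to be the far larger exclusion, since planned attrition leaves 0.89⁵ = 55.8%. All of this stands and limits the weight of the point. None of it returns an implanted violator to the primary rate, and correcting the completer rule would leave the eligibility clause in force.

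A reader might infer four stronger things that the documents do not support:

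- **That the rule inflates the rate.** It does so only if violators have more complications than eligible subjects, and no section says they do.
- **That subjects can be ruled ineligible once their complication is known.** Section 9.1 says "Some examples of data that may be monitored remotely include: informed consent forms, enrollment, eligibility, implant", but it does not place eligibility review after events, and it asks for timely upload of source documents. Eligibility is fixed at consent under 3.5.1. The opportunity is not documented.
- **That the Kaplan-Meier curve also drops violators.** The word enrolled in 2.5.4 sits in a censoring rule, and 2.3.7 sets no eligibility condition. The population is unclear, which is all that can be said.
- **That the error is 3.5% or 6.4% in the 15% scenarios.** Those values keep n at 979 after the violators have been taken out of it. With n reduced they are 2.9% and 5.1%.

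**Conclusion.** The point holds for primary endpoint 3. As written, 2.3.4 leaves out implanted subjects who breached a criterion, together with their lead complications, and it disagrees on eligibility with 2.3.5, which uses the same complications. The effect is confined to the primary 5-year rate: violators who complete 60 months still count in endpoints 7 and 8.

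The size and direction of any bias cannot be determined from the documents. The figures of 2.9% and 5.1% rest on an assumed 2% or 5% of violators, an assumed 15% complication rate among them, an all-implanted rate exactly at the goal, and violators coming out of the 979. With equal rates there is no inflation. The case for changing the plan rests on the population being wrong for a safety rate and on the inconsistency between sections. It does not depend on a demonstrated bias.

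**What to change.** - **2.3.4:** delete the condition of having met the enrollment criteria, so that every consented subject implanted with a Sentus QP lead is in the endpoint 3 population whatever the eligibility finding. This aligns it with 2.3.5 on eligibility; 2.3.5 needs no change on this point.
- **2.5.4:** state that the Kaplan-Meier curve covers all implanted subjects.
- **Reporting:** list eligibility violators with their outcomes, and give the eligible-only rate as a supportive analysis.

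The cost is a clause in 2.3.4, a sentence in 2.5.4, one listing and one supportive analysis. No new data are needed, since these subjects are already followed, and 979 and 1754 stand. The downside is that the reported rate may be slightly less favourable.
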